1.6	10-26-2009	Clarify size criteria for Inclusion Criteria #1
1.7	01-26-2011	Addition of angiotensin-2 biomarker testing, formatting and administrative changes
1.8	06-05-2018	Updated Objectives based on availability of data

SYNOPSIS

PROTOCOL SYNOPSIS	
Study Number	SCI 07-001.1
Title	A Phase II Biomarker Trial Of Gelatin Encapsulated Extract Of American Ginseng Root (LEAG) In Breast Cancer.
Clinical Phase	Phase II
Objectives	
Primary	To analyze the serum and in vivo tissue biomarker response of breast cancer tumor and surrounding normal breast epithelial cells to preoperative treatment with gelatin encapsulated lyophilized water-extract of American Ginseng root (LEAG).
Secondary	To compare before and after administration of LEAG responses on a proteomic panel of inflammatory mediators.
	To establish a base of comparison of biomarkers between breast cancer patients and the database of women with increased breast cancer risk in the Surrogate Endpoints and Lifestyle Factors (SELF) study.
Study Agent	New chemical entity (NCE): A gelatin encapsulated standardized lyophilized water-extract of American Ginseng root derived from Panax quinquefolius , L. (LEAG) (250 mg per capsule). Treatment dosage is 1 gram per day (4 capsules per day).
Study Population	A total of 25 to 50 female patients age ≥ 18 . New diagnosis of breast cancer with biopsy showing invasive or non-invasive breast cancer (DCIS) at least 0.5cm greatest diameter on imaging. Surgical patients undergoing lumpectomy, subtotal, or total mastectomy are eligible.
Design	Single Center, Non-Randomized, Unblinded, Investigator Initiated Phase II biomarker Trial.
Intervention	A total of 1 gram of LEAG per day for a minimum of 5 days and a maximum of 14 days. Four 250 mg capsules taken with food in the morning.
Treatment Group	Surgical resection alone. For 5 to 14 days preceding their scheduled surgical procedure, the patient will be treated with a total of 1 gram of LEAG per day. Subjects must complete a minimum of 5 days of treatment with LEAG prior to day of surgery.

Study Evaluations	The diagnostic core biopsy specimen will be compared to the operative specimen for the following:
Primary Objective Evaluations	Proliferation Markers: Immunohistochemistry for ER, PR, Ki67, cyclin D1, COX-2
	Angiogenesis Marker: Angiopoetin 2
Secondary Objective Evaluations	
	Evaluate changes in inflammatory mediator proteinomic panel (adiponectin, CRP, HGF, IGF-1, IGF-1R, IL-10, IL-12p40, IL-1b, IL-1ra, IL-2, IL-23, IL-4, IL-6, IL-8MCP-1, TGFb1, TNFa).
	Establish a comparison of biomarkers between breast cancer patients and the database of women with increased breast cancer risk in the SELF study.
	Collect anthropometric data (height, weight, body composition, waist-hip ratio), dietary history, exercise habits, insulin resistance blood panel (HOMA index, leptin, ghrelin, and adiponectin) and Gail Score.
Hypothesis	LEAG will have an anti-proliferative effect on human breast tumors and benign breast epithelia. LEAG may favorably alter biomarkers of inflammation and the metabolic syndrome.
Safety Considerations	All patients will be monitored for toxicity related to therapy. Adverse events will be collected through the post-surgery visit and all related or possibly related adverse events for 30 days following discontinuation of LEAG therapy or until resolution or stabilization of the adverse event. Discontinuation of treatment will be considered in patients experiencing excessive toxicity.
Statistical Considerations	High variability among tumors in the patient population is anticipated. Each patient will serve as her own control; pre-treatment biopsy tissue will be compared to post-treatment surgical tissue. Descriptive statistics including the mean, median, range, standard deviation, interquartile range, skewness, and kurtosis will be calculated for each measure. Paired t-tests, or Wilcoxon signed-rank tests, depending on the distributional characteristics of the variables, will be used to assess changes in biomarkers from biopsy to surgery. In order to examine the inter-relationships between the anthropometric data, the cytological markers, serum ginsenoside concentrations, and a panel of inflammatory serum proteins, data visualization techniques will be employed. Correlation coefficients will be used to summarize linear relationships between continuous measures. Regression techniques will be used to model nonlinear relationships. All statistical procedures will be performed in consultation with the Division of Statistics and Research Consulting at SIU School of Medicine.

Timeline	Patient enrollment and data collection are expected to be complete within 72 months.
-----------------	--

TABLE OF CONTENTS

	Page
SYNOPSIS	i
SCHEMA	vii
1.0 OBJECTIVES	1
1.1 Primary Objectives	1
1.2 Secondary Objectives	1
2.0 BACKGROUND	2

1.0 OBJECTIVES

1.1 Primary Objectives

Analyze biomarker *in vivo* response of breast cancer tumors and surrounding normal breast epithelial cells to preoperative treatment with gelatin encapsulated lyophilized water-extract of American Ginseng root (LEAG).

- 1.1.1 The diagnostic core biopsy will be compared to the operative specimen for effects on the following proliferative and tumor biomarkers: immunohistochemistry for ER, PR, Ki67, cyclin D1, COX-2.

1.2 Secondary Objectives

- 1.2.1 To compare before and after administration of LEAG responses on a proteomic panel of inflammatory mediators.
- Evaluate changes in inflammatory mediator proteomic panel (adiponectin, CRP, HGF, IGF-1, IGF-1R, IL-10, IL-12p40, IL-1b, IL-1ra, IL-2, IL-23, IL-4, IL-6, IL-8, MCP-1, TGFb1, TNFa). insulin, ghrelin and leptin; measured at baseline and after 5-14 days of treatment.
 - Measure angiogenesis marker, angiopoietin 2.
- 1.2.2 In a preliminary manner compare the Gail risk model, anthropomorphic measurements, dietary history, exercise habits, and biomarkers of insulin resistance between breast cancer patients in this study and our database of women with increased breast cancer risk participating in the ongoing Surrogate Endpoints and Lifestyle Factors (SELF) study.
- Collect anthropometric data (height, weight, body composition, waist-hip ratio, BMI), dietary history and exercise habits using the same instruments, as our SELF study (Appendices A, B, and C) at baseline.
 - Calculate the homeostasis model assessment (HOMA) index [insulin resistance (HOMA-IR) = fasting insulinemia (mU/mL) × fasting glycemia (mmol/L)/22.5] (collected fasting on the day of surgery).
 - Measure serum leptin, ghrelin, and adiponectin levels (collected fasting on the day of surgery).
 - Evaluate Breast cancer risk assessment through calculation of a Gail Score (Appendix D)

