5.0 TREATMENT PLAN

5.1 Screening Procedures

- 5.1.1 History and physical reviewed and recorded, including performance status.
- 5.1.2 Concomitant medications reviewed and recorded.
- 5.1.3 Vital signs reviewed and recorded.
- 5.1.4 Inclusion and exclusion criteria will be reviewed.
- 5.1.5 Review and record available HbA1c status (within past 60 days) or fasting blood glucose values (three consecutive days below 140 mg/dl)
- 5.1.6 Informed consent process
- 5.1.7 Pregnancy test, if required

5.2 Study Visit 1

- 5.2.1 Obtain tissue blocks for immunohistochemistry from core biopsy

- Proliferation Markers: immunohistochemistry for ER, PR, Ki67, cyclin D1, Cox-2, and angiotensin 2.
- Cytotoxicity Markers: cyclin D2 and TUNEL
- Angiogenesis Markers: angiotensin 2

5.2.2 Fasting lab work will be obtained.

Serum for levels of gRc and gRh2, inflammatory mediator proteomic panel (IL1b, IL6, IL8, MCP-1, TNFa, HGF, NGFb, Insulin, and Leptin), pregnancy test (if not already done at screening visit) if woman is of child-bearing potential, HOMA index, leptin, ghrelin, and adiponectin.

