5.3 Treatment Regimen

5.3.1 Patients will be treated with ginseng for 5 to 14 days prior to surgery. The final dose of LEAG will be administered the day prior to surgery as surgical patients are asked to abstain from food and drink (excluding water) over night prior to surgery.

- 5.3.2 Patients will take four, 250mg tablets daily.
- 5.3.3 Patients will be given a drug diary to record dates of ginseng therapy in order to monitor compliance.
- 5.3.4 Because ginseng has a rare risk of lowering the blood sugar level, patients with diabetes (as defined by the American Diabetes Association) will be encouraged to use their home blood glucose machine to monitor their blood sugar twice a day during treatment and report any readings less than 60. Patients without a home monitoring device will be instructed to report any signs or symptoms of hypoglycemia such as lightheadedness, sweating or confusion. Patients will be provided a diary to track their twice daily glucose checks.
- 5.3.5 Because ginseng has been reported to alter blood pressure and heart rate, patients being treated for hypertension will be encouraged to report any changes of blood pressure greater than 20 mmHg increase from baseline. Patients should be encouraged to have blood pressure readings daily. Patients will be provided with a diary (Appendix I) and a blood pressure monitoring system to record daily blood pressure measurements. If preferred, patients may use their own home monitoring device or use a monitor found at a local drug store.

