5.5 Day of Surgery Visit

- 5.5.1 Repeat fasting lab work.
- 5.5.2 Obtain tissue samples during scheduled surgery.
- 5.5.3 Review and complete drug accountability and calculate compliance. Collect Ginseng medication diary and any unused study drug.
- 5.5.4 Obtain vital signs.
- 5.5.5 Complete performance status evaluation.

- 5.5.6 Review and complete adverse event log.
- 5.5.7 Review and record concomitant medications.
- 5.5.8 Collect, review and record blood pressure and/or blood sugar diaries (Appendix I), if indicated.

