9.0 LABORATORY TESTS AND METHODS

9.1 Blood Collection

Collection of blood for inflammatory mediators and HOMA index must occur within 2 weeks of treatment. Participants will have blood drawn prior to starting ginseng and on the day of surgery.

A. Fasting Blood Draw (NPO after midnight):

1. Draw 40 cc blood from a vein into vacutainer tubes: 6mL in EDTA, 6mL in Na Heparin, 5mL in clot activator tube, and 24mL in serum tubes. (Serum tubes to be refrigerated (4°C) until centrifuged, and then serum will be aliquoted into 1ml cryotubes).
2. An additional 2 tubes of blood with citrate will be drawn on the first five patients for the Platelet Function Assay-100. – See section 5.7.4
3. Serum for ginsenoside levels and inflammatory proteins stored in -80°C freezer in lab prior to shipping to Carbondale laboratory.
4. Analyze serum for HOMA index, leptin, ghrelin, adiponectin, and angiopoietin.

5. Analyze serum for gRc and gRh2, IL1b, IL6, IL8, MCP-1, TNFa, HGF, NGFb, insulin, leptin.

B. Inflammatory Serum Protein Panel (LINCOpex) and Serum Adipokine Panel

Serum levels of TNFa and IL6 are elevated in patients who are obese or hyperinsulinemic and play an important role in the pathogenesis of type II diabetes. These serum markers also declined in insulin-resistant individuals who participated in an exercise program (48). In a study of adipokine expression in cancer patients, breast and colorectal cancer patients had blood plasma levels of insulin, TNF-alpha and breast epithelial expression of estrogen and progesterone receptors higher than controls. In the same study, breast cancer patients, but not colorectal cancer patients, had plasma levels and adipose tissue expression of leptin significantly higher than controls, associated with elevated values of estrogen and progesterone-receptors (49). These serum markers can be assayed simultaneously in a multiplex immunoassay (human adipokine panel B, LINCO, St. Louis, MO) using Luminex technology. The assay will be performed by the SIU Cancer Institute Molecular Core Facility. Serum adipokine levels of breast cancer patients before and after ginseng treatment will be compared. Serum will be collected and stored at -80°C until the assay is performed.

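### Objective 1.2.2 ties the SELF comparison of HOMA-IR, leptin, ghrelin and adiponectin to a post-LEAG sample, although a pre-LEAG fasting sample is already scheduled

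*Combined protocol and SAP*

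**What the plan says.** Objective 1.2.2 (section 1.2, Secondary Objectives) sets trial patients against women in the SELF database on Gail risk, body measurements, diet, exercise and markers of insulin resistance. Its items do not share one time point:

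- Body measurements, diet and exercise are pre-treatment: "dietary history and exercise habits using the same instruments, as our SELF study (Appendices A, B, and C) at baseline".
- HOMA-IR is not; its formula ends "fasting glycemia (mmol/L)/22.5] (collected fasting on the day of surgery".
- The other three markers are not either: "Measure serum leptin, ghrelin, and adiponectin levels (collected fasting on the day of surgery".

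The surgery-day sample is a post-treatment sample. Section 5.3.1 gives LEAG for 5 to 14 days and adds: "The final dose of LEAG will be administered the day prior to surgery".

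Elsewhere the protocol schedules the same analytes before treatment. The fasting labs at Study Visit 1 (section 5.2.2) include "HOMA index, leptin, ghrelin, and adiponectin". Section 9.1 says: "Participants will have blood drawn prior to starting ginseng and on the day of surgery". Section 5.5.1, for the day of surgery, says "Repeat fasting lab work". The calendar in section 12.0 marks the fasting draw at Study Visits One and Two. Objective 1.2.1 includes adiponectin in its panel and adds "insulin, ghrelin and leptin; measured at baseline and after 5-14 days of treatment".

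Section 16.0 specifies paired tests of change from biopsy to surgery, descriptive statistics, correlations and regression. It gives no method for the SELF comparison and does not say which sample enters it.

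**The concern.** Section 2.4 explains that the comparison is meant to provide a reference point between women with breast cancer and women in SELF. That calls for patients as they were before the study drug. Objective 1.2.1 treats the effect of LEAG on adiponectin, insulin, ghrelin and leptin as an open question. Using post-LEAG values in 1.2.2 assumes that the answer is no effect.

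An analyst who follows 1.2.2 literally would compare treated patients with SELF women, who, as far as section 2.4 lets one infer, took no LEAG. A difference, or its absence, could then reflect the disease, the extract, or both. If LEAG lowers insulin resistance, for example, an excess in cancer patients would be understated.

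**Working it through.** **Text check.** The protocol states no figure for the SELF comparison, so there is none to reproduce.

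| Place | Sample for the four markers |
|---|---|
| 1.2.2 | Day of surgery only |
| 1.2.1 | Before and after treatment (adiponectin, insulin, ghrelin, leptin) |
| 5.2.2 | Study Visit 1, all four |
| 5.5.1 | Day of surgery, as a repeat |
| 9.1 | Before LEAG and day of surgery |
| 12.0 | Visits One and Two |
| 16.0 | Silent on the SELF comparison |

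Only 1.2.2 attaches a timing to these markers for the SELF comparison, and it is the post-treatment one.

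**What the choice does.** In expectation,

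patient(post) − SELF = [patient(pre) − SELF] + [patient(post) − patient(pre)].

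The last bracket is the bias: any LEAG effect plus any time or perioperative change. With the Visit 1 sample it drops out.

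**Inputs for an illustration.** The number of patients, n = 25 to 50, is from section 16.1. The following are assumptions, because the documents give no values: m = 50 to 200 SELF women, a mean shift d of 0.1, 0.2 or 0.3 SD, equal SDs in both groups, and Visit 1 values missing at random.

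**Bias against precision.** In SD units, SE = √(1/n + 1/m).

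| n, m | SE | d/SE, d = 0.1 | d = 0.2 | d = 0.3 |
|---|---|---|---|---|
| 25, 50 | √0.060 = 0.245 | 0.41 | 0.82 | 1.22 |
| 25, 200 | √0.045 = 0.212 | 0.47 | 0.94 | 1.41 |
| 50, 50 | √0.040 = 0.200 | 0.50 | 1.00 | 1.50 |
| 50, 200 | √0.025 = 0.158 | 0.63 | 1.26 | 1.90 |

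**If some Visit 1 values are missing.** Let k patients have one.

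- Mean squared error, surgery-day sample with all n: d² + 1/n + 1/m.
- Mean squared error, Visit 1 sample with k: 1/k + 1/m.
- Visit 1 is better when k > 1/(d² + 1/n), whatever m is.

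| d | n = 25 | n = 50 |
|---|---|---|
| 0.1 | 1/0.05 = 20.0, so 21 | 1/0.03 = 33.3, so 34 |
| 0.2 | 1/0.08 = 12.5, so 13 | 1/0.06 = 16.7, so 17 |
| 0.3 | 1/0.13 = 7.7, so 8 | 1/0.11 = 9.1, so 10 |

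With complete Visit 1 values (k = n) nothing is lost at any d.

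**Precision lost at 80% availability (k = 0.8n).** The SE ratio is √[(1/k + 1/m)/(1/n + 1/m)]:

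- 25, 50: √(0.070/0.060), a rise of 8.0%
- 25, 200: √(0.055/0.045), a rise of 10.6%
- 50, 50: √(0.045/0.040), a rise of 6.1%
- 50, 200: √(0.030/0.025), a rise of 9.5%

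**The case against.** The strongest reply is that the harm depends on two conditions the documents do not establish: that the surgery-day value is the one analysed, and that it differs systematically from the Visit 1 value. Objective 1.2.2 says when blood is collected, not which value is analysed, and both samples are planned. The hypothesis in the synopsis says only that LEAG may alter such markers. The human glycaemic data in section 2.4 are postprandial, 40 minutes after a dose, not fasting. All of this stands, and it limits the claim to a conditional one. It does not remove the conflict, because no other section tells the analyst to set the 1.2.2 timing aside.

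A second reply is that planned samples may not exist. Version 1.8 revised the objectives according to what data were available, and the protocol does not say whether that explains this timing. Visit 1 glucose, needed for HOMA-IR, is a particular uncertainty. This also stands, and is why the fix asks for counts per marker.

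A third is that surgery secures the overnight fast. Both draws are specified as fasting from midnight, so the protocol gives no ground for preferring one. Imperfect fasting at Visit 1 is possible, though, and the calculation above does not allow for it.

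Finally, no between-group test is planned, so ratios of bias to standard error only indicate scale. That is correct. It is also fair that the lack of any SELF method in section 16.0 is a wider gap, of which this is one part.

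**Conclusion.** The concern holds. The wording conflict is certain. Objective 1.2.2 names a post-LEAG sample for all four markers, four other places in the protocol (5.2.2, 5.5.1, 9.1 and the calendar) provide for a pre-LEAG one, and section 16.0 does not choose between them. If the named sample is used, the patient-SELF difference carries the whole change on treatment, which the planned Visit 1 sample would avoid.

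The size of that change is unknown and may be zero. Under the assumptions stated, shifts of 0.1, 0.2 and 0.3 SD amount to 0.4–0.6, 0.8–1.3 and 1.2–1.9 standard errors. The point should be fixed but is not critical: the objective is secondary and preliminary, no primary conclusion depends on it, and other differences between patients and SELF women, such as age and BMI, remain whichever sample is used.

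**What to change.** - In section 16, state that the SELF comparison of HOMA-IR, leptin, ghrelin and adiponectin uses the fasting values from Study Visit 1, taken before the first dose of LEAG.
- In 1.2.2, replace both surgery-day phrases with a reference to that sample. Keep the surgery-day values for the before/after analysis in 1.2.1.
- Report, for each marker, how many patients have a Visit 1 value. Where it is missing, show the surgery-day value descriptively, labelled post-LEAG, and do not pool it with Visit 1 values.
- If the surgery-day timing was chosen because Visit 1 data are lacking, say so in the text.

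The cost is one sentence and two phrases, with no new visit or blood draw. The downside is a possible loss of evaluable patients. At 80% availability the standard error rises by about 6–11%. For a shift as small as 0.1 SD, the Visit 1 sample gives the lower mean squared error only with at least 21 of 25 or 34 of 50 patients.

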2.0 BACKGROUND

2.1 Breast Cancer, Problem and Relevant Cancer Biology

With the aging demographics of this country, breast cancer incidence is expected to double over the next 15 years, bringing prevention efforts to the forefront (1). Current prevention methods include chemoprevention with the selective estrogen receptor modulator, tamoxifen, versus oophorectomy or prophylactic mastectomy. While effective, these measures entail potential adverse effects. Greater than 90% of women with breast cancer risk profiles high enough to consider chemoprevention with tamoxifen decide against taking it. In contrast, there is strong public acceptance of dietary supplements such as soy and green tea which are perceived as safe and health-promoting. An ideal breast cancer prevention agent would be a safe nutritional intervention that could also have additional metabolic benefits. Western women have the highest incidence of breast cancer in the world, and since less than ten percent of breast cancer is attributed to known genetic causes, nutrition and lifestyle are suspected to be significant factors contributing to this risk. The raised incidence of breast cancer in Western countries parallels the prevalence of the so-called metabolic syndrome, the major components of which are obesity, hyperinsulinemia, dyslipidemia, and atherosclerosis. It is an open question whether these two trends are biologically linked (see discussion below). Our study aim is to evaluate whether the gelatin encapsulated lyophilized water-extract of American Ginseng root (LEAG) is a potential breast cancer prevention agent and is able to directly affect both breast cancer cell proliferation in newly diagnosed tumors, as well as positively influence the inflammatory mediators potentially involved in obesity associated pathways that may increase the risk of breast cancer.

2.2 Adiposity, Diet, Diabetes, Hyperinsulinemia and Breast Cancer Risk

There are several lines of epidemiological evidence that Western diet and lifestyle influence the increased rate of breast cancer. Asian women, who have some of the lowest rates of breast cancer in the world, acquire a risk level approximating the national average over several generations after immigrating to the United States (2). The pattern of factors associated with breast cancer incidence in Western countries parallels the major components of the insulin resistance syndrome: hyperinsulinemia, dyslipidemia, hypertension and atherosclerosis. High total energy intake and decreased physical exercise lead to excess adipose tissue, which increases free fatty acids and tumor necrosis factor alpha (TNF α) (3). These two components may be involved in the pathogenesis of hyperinsulinemic glucose intolerance in genetically predisposed individuals as they grow older (4).

It is generally agreed that obese women are at increased risk for postmenopausal, but not premenopausal, breast cancer. A plausible mechanism that could link obesity to breast cancer may be that mammary carcinogenesis is promoted in obese post-menopausal women as a result of synergistic activity between the concomitants of hyperinsulinemia, such as insulin-like growth factor (IGF) increase, and increased estrogen concentrations derived from aromatization in adipose tissue. In addition to these facts, it is now proposed that a third mechanism is plausible.

Excess energy intake and resultant hyperglycemia can cause up-regulation of phosphoinositide 3-kinase (PI3-K) signaling via its two downstream effector serine-threonine protein kinases, Akt and the mammalian target of rapamycin (mTOR). Akt and mTOR are known to have oncogenic properties mediated in part by suppression of apoptotic signals and in addition by their effects on cell cycling. In obese humans increased PI3K signaling may lead to mitochondrial damage and be part of the pathway of mammary carcinogenesis inducing ductal hyperplasia and DNA damage through oxidative stress.

The observation that tumors utilize glucose more avidly than normal tissues dates back to 1964 (5) and since then has prompted a number of epidemiologic studies comparing breast cancer rates among subjects with diabetes versus those with normoglycemia. Retrospective studies show a mild positive correlation (RR 1.2-2.0), but researchers admit that confounding variables such as the lower consumption of alcohol among diabetics versus non-diabetics tend to weaken the association (6). While studies to date seem to show a mild increased risk of breast cancer associated with type II diabetes, the potential impact from a prevention perspective is increased by a number of considerations. The prevalence of obesity and type II diabetes in the United States has doubled in the decade since the Atherosclerosis Risk in Communities Study commenced, and even a mild correlation could account for more than 10% of the breast cancer diagnoses in this country per year (5). Persons who are not yet diabetic or obese but who have a predisposition as evidenced by overweight (BMI > 25 but < 30) account for as much as 35% of the U.S. population. The study we are proposing looks at the potential reversibility of the epithelial lesions associated with diet induced obesity and diabetes.

Epidemiological reports are inconsistent on the association between breast cancer risk and the dietary intake of either individual fatty acids or of antioxidant vitamins. The inconsistencies may in part be due to interactions between the two classes of nutrients at the level of the cell membrane, affecting their potential role in mammary carcinogenesis. The effects of specific dietary fatty acids and antioxidant vitamins on experimental mammary cancer systems have been compared with reported epidemiological associations of the same agents with breast cancer risk in humans (7). An increased ratio of n-3 to n-6 polyunsaturated fatty acids (PUFAs) in the diet inhibits the growth of a rat mammary cancer model. There is also evidence that members of the n-3 PUFA series can inhibit the growth of human breast cancer cells both in vitro and in explants. Clinical trials of supplementary n-3 PUFAs in conjunction with a reduced fat intake have been proposed for breast cancer prevention. In particular, it is suggested that n-3 PUFAs have an inhibitory effect on COX-2 activity (8).

